7.3. Early Study Termination

The study may be terminated early if the extent (incidence and/or severity) of emerging effects/clinical endpoints is such that the risk/benefit ratio to the study population as a whole is unacceptable. In addition, further recruitment in the study overall or at a particular study site may be stopped due to insufficient compliance with the protocol, Good Clinical Practice (GCP) and/or other applicable regulatory requirements, due to procedure-related problems or if the number of discontinuations for administrative reasons is too high. Sites must refer subjects for ongoing psychiatric care if the study is terminated early.

8. STUDY ASSESSMENTS AND PROCEDURES

The Schedule of Activities (Table 2) summarizes the study assessments/procedures to be performed at each visit. Individual assessments and procedures are described below.

It may be necessary to perform these procedures at unscheduled time points if deemed clinically necessary by the Investigator. Furthermore, additional evaluations/testing may be deemed necessary by the Investigator and/or the Sponsor for reasons related to subject safety. In some cases, such evaluation/testing may be potentially sensitive in nature (e.g., testing for human immunodeficiency virus [HIV], hepatitis C virus [HCV], etc.), and thus local regulations may require that additional informed consent be obtained from the subject. In these cases, such evaluations/testing will be performed in accordance with those regulations.

Sites may begin using the optional Prescreen assessments described within this protocol upon all regulatory approvals and Part 1 site activation.

Changes that may be implemented, if needed, due to the coronavirus disease 2019 (COVID-19) pandemic are described in Section 9.8.

8.1. Administrative Procedures

8.1.1. Informed Consent

For this study, the subject must be cognitively able to understand the requirements of the study and provide the informed consent to participate in the study; use of a legally authorized representative to provide consent to participate is not allowed.

Informed consent forms (ICFs), any subsequently revised written ICFs, and any written information provided to the subject must receive Institutional Review Board (IRB)/Institutional Ethics Committee (IEC) approval in advance of use. The subject should be informed in a timely manner if new information becomes available that may be relevant to the subject's willingness to continue participation in the study. The communication of this information will be provided and documented via a revised main ICF or addendum to the original ICF that captures the subject's dated signature.

The ICFs will adhere to IRB/IEC requirements, applicable laws and regulations and Sponsor requirements.

8.1.1.1. Prescreen Informed Consent (Optional)

Informed consent must be obtained from each potential subject prior to the collection of any information about them during the Prescreen process. Prescreen consent may be obtained via a signed consent form or verbal consent over the phone per the standard practice of the individual site.

8.1.1.2. Main Informed Consent

Documented consent must be obtained from each potential subject prior to participating in study procedures. The subject will be given sufficient time to read the ICF(s) and the opportunity to ask questions. Consent must be documented by the subject's dated signature on

MM-120 (LSD) Clinical Study Protocol: MMED008

the ICF(s) along with the dated signature of the person conducting the consent discussion. The ICF(s) that is/are used must be approved by both the sponsor and by the reviewing IRB.

A copy of the signed and dated ICF(s) should be given to the subject before participation in the study.

Subjects will be asked to inform their care provider(s) that they are considering taking part in the study to ensure that the subject's care providers are able to appropriately monitor the subject during the study including during any required tapering of prohibited concomitant medications.

8.1.1.3. Real World Evidence

At the beginning of the study participants will be invited to opt into a service which can link existing health data with the participant to enrich data collected in the study. In order to link traditional study data to Real World Data (RWD), a common, universal ID (herein named a "token") that is unique to each study subject, persistent, and also available in real-world datasets will be used. A token is a universal, de-identified key that can be used to reference participants across datasets, created based on elements of patient personal identifying information (PII) using privacy-preserving technology from vendor The key features below make tokens a secure and consistent mechanism for linking real world healthcare data sources at the patient level while preserving the privacy of trial participants.

- Tokens are irreversible and blinded: Hashing by technology destroys the input PII, which makes tokens de-identified. The input PII cannot be backward-engineered from the output token.
- Tokens are unique: Each token is unique to the input PII, avoiding false matches.
- Tokens are consistent: The same set of input PII will always create the same tokens. Tokens created in any dataset are compatible and can be matched to one another.
- Tokens are compliant with trial regulation: A participant's PII never leaves the site.
- Multiple tokens derived from different PII elements are created for each subject to enable accurate matching (avoiding false positives and limiting false negatives).

At the time trial participants are screened for enrollment into the study, participants will be offered the consent for tokenization and linking of their clinical trial data. Outside of tokenization and linking of their clinical trial data, no additional study procedures beyond what is outlined in this study protocol, would be completed as result of their participation. Participation in tokenization is optional and participants who decline to participate in the tokenization process will still be able to participate in the study. The trial participant's tokenized data will be available for linking to other future data indefinitely or until they withdraw their consent for future data linking. The participant will be instructed of the withdrawal consent process with information provided in the ICF.

8.1.2. Demographics

The following demographics will be recorded: year of birth, self-identified gender, sex at birth, race and ethnicity.

For the purposes of demographics, both sex at birth (e.g., male, female) and self-identified gender (e.g., male, female, non-binary) should be recorded. This is because normal ranges for some clinical laboratory and ECG parameters, scoring from some questionnaires and the ability to become pregnant are based on a binary male/female designation while other parameters such as baseline symptom scores for anxiety and depression are expected to correlate to gender identity. Further, selected dosing session monitors should be aligned with gender identity and not sex at birth.

8.1.3. Prescreen Assessment (Optional)

Per the Schedule of Activities (Table 2) limited activities are planned for the optional Prescreen. Verbal consent must be collected before any Prescreen information is collected (see Section 8.1.1.1). Sites that choose to participate in the optional Prescreen will be provided a checklist with detailed instructions including prompts for collecting demography, an abbreviated Medical History and Concomitant medication review. Sex at birth, age, weight and height will be collected (an estimate of weight and height can be made for a phone screen), and BMI will be determined via calculation. The MINI can also be administered by qualified site personnel at the Prescreen.

Note: Information captured during the Prescreening assessments will not be captured in the EDC.

8.1.4. Eligibility Assessment

All inclusion criteria (listed in Section 5.1.1) and exclusion criteria (listed in Section 5.1.2) will be reviewed by the Investigator or qualified designee at Screening (Visit 1), Baseline (Visit 2) and Day 1/Randomization (Visit 3A), prior to randomizing the subject, to ensure that the subject qualifies for the study, however, of the vital signs taken at Visit 3A only temperature and blood pressure will be used to confirm final eligibility against inclusion/exclusion criteria.

All inclusion criteria must be met and none of the exclusion criteria may apply for the potential subject to be eligible to participate in the study. No eligibility waivers (or other protocol waivers) will be granted.

Subjects found ineligible during review of inclusion/exclusion at any of these visits will not proceed through the remaining screening process, except in cases of rescreening as described in Section 5.3.

Eligibility at Visit 3a/Randomization includes:

- 1. Review medical, psychiatric, and medication history
- 2. Vital signs (BP, HR, RR, temperature) within 1 hour of dose administration; Temperature and blood pressure (only) will be used to determine eligibility at Visit 3a. Systolic blood pressure >140 mmHg or diastolic blood pressure >90 mmHg

(confirmed by 3 separate readings) will make the participant ineligible for dosing. Temperature over 37.78°C (100°F) would be indicative of an acute illness and would make the subject ineligible for dosing.

• A positive pregnancy test will make the participant ineligible for dosing.

4. C-SSRS-SLV version

• Active suicidal ideation will make the participant ineligible for dosing as evidenced by a "Yes" in response to C-SSRS suicidal ideation question 4 or 5

8.1.5. Medical/Psychiatric and Medication History

Medical/psychiatric and medication history will be assessed during Screening (Visit 1) and recorded in the eCRF. However, if information about the subject's medical/psychiatric and medication history is learned during the course of the study, this will also be recorded in the eCRF, even if this history is learned after Screening (Visit 1).

The medical/psychiatric history will be obtained by the Investigator or qualified designee. Medical/psychiatric history will include all chronic, past and ongoing conditions, regardless of the year diagnosed. To confirm eligibility criteria, the medical/psychiatric history will include, but is not limited to, a review of the following: suicidal ideation or behaviors; neurological or psychiatric disorder(s); family history of relevant psychiatric and medical concerns; major traumas; surgeries; any clinically significant diseases of the renal, hepatic, gastrointestinal, cardiovascular, or musculoskeletal system; clinically significant immunological, endocrine, or metabolic diseases; infection with HIV, hepatitis B and hepatitis C. Sites should make an effort to obtain medical and/ or psychiatric records for subjects.

All therapies (prescription or over-the-counter medications, including vaccines, supplements; non-pharmacologic therapies such as electrical stimulation, acupuncture), other than the study intervention will be assessed as part of the subject's medical and medication history. Medication history will include a description of the type of therapy, duration of use, dosing regimen, route of administration, and reason for use. Sites should make an effort to obtain pharmacy records for subjects.

8.1.6. Medication Taper

Medication tapers will be required for any subject on a prohibited medication for the following reasons:

- to eliminate potential confounding efficacy in the statistical analysis.
- to mitigate the risk of serotonin syndrome, and
- to eliminate the pharmacologic effects of potent 2D6 inhibitors.

The study site designated physician must monitor study subjects throughout the taper and through the end of the study or early termination.

Any prohibited anxiolytics, antidepressants or other medications, supplements or therapeutics (over-the-counter or prescribed) used to treat anxiety, depression or other mood disorders, as well as any other substances, supplements etc. that may confound the results of the study (as described in Section 6.10.1) will be tapered prior to Baseline (Visit 2). Subjects on such prohibited medications/substances at the time of Screening (Visit 1) will undergo a medication taper prior to advancing to Baseline (Visit 2), if safe for the subject, in the opinion of the Investigator. Medication tapering will be done with oversight from the study site designated physician; for subjects on prescribed medications to treat anxiety, depression or other mood disorders, the medication taper will be overseen by the study site designated physician based on acceptable local practice standards.

The last dose of the substance being tapered must have been taken no closer to Baseline (Visit 2) or Day 1/Randomization (Visit 3A) than indicated by the prohibition period described in Table 5. If the medication taper is anticipated to require more time than is available in the subject's remaining screening period, the subject will need to be screen-failed, and will need to rescreen.

Confirmation of eligibility is required at Baseline (Visit 2) and Day 1/Randomization (Visit 3A), including confirmation of a negative urine dipstick drug screen at these 2 visits and confirmation that the subject is no longer taking any prohibited medications/substances.

Additionally, subjects must also avoid starting, stopping or altering non-medicinal therapies/activities from the time of providing informed consent until End of Study, as described in Section 5.2.3.

Note: It is not permitted to stop/taper medications being used to treat excluded conditions.

8.1.7. Concomitant Medication Review/Collection

Concomitant therapies will be recorded throughout the study, beginning at the time of ICF signing until End of Study (Week 12 [Visit 9] or Early Withdrawal).

Medications taken at Baseline (Visit 2) or any time after, including those between visits regardless of whether the subject is on the medication at the time of the site visit, will be recorded in the concomitant medication eCRF. Medications stopped prior to Baseline (Visit 2) are recorded in the medication history eCRF.

Non-medicinal therapies/activities (see Section 5.2.3) will also be recorded throughout the study, beginning at the time of ICF signing until End of Study (Week 12 [Visit 9] or Early Withdrawal).

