Timing or Permitted Window	none	Up to 30 days prior to Baseline	1-5 days prior to Day 1 ^{b, c}	Pre- dose	Dosing & post- dose	1 day after dosing	Day 8 ± 1 day	Day 15 ± 3 days	Day 29 ± 3 days	Day 57 ± 5 days	Day 85 ± 5 days
Administrative Procedures											
Prescreen Informed Consent	X										
Informed consent		X									
Demographics	X	X									
Eligibility assessment		X	X	X							
Medical psychiatric and medication history ^d	X	Medical/psychiatric and medication history will be collected via interview at Screening [Visit 1] if information about the medical/psychiatric and medication history is learned during the course of the study, this will also be recorded, even if first learned after Screening [Visit 1].									
Medication taper (if applicable)		X									
Concomitant medication & non-medicinal therapy collection	X		Medications/non-medicinal therapies used at Baseline [Visit 2] or any time after, including those taken between visits, regardless of whether the subject is on the medication/therapy at the time of the site visit, will be recorded in the designated CRF. Medications/therapies stopped prior to Baseline [Visit 2] are recorded in medication history.								
Randomization				X							
Clinical Procedures/Assessmo	ents										
Physical examination		X				X					X
Neuropsychiatric examination			X			X	X	X	Х	X	X
Vital signs ^e (BP, heart rate, respiration rate, temperature)		X	X	Xf	X	X	X	X	Х	Х	X
Weight	Xg	X									
Height	Xg	X									
BMI	X	X									
12-lead safety ECG		X	X			X					
Adverse event collection		AEs are evaluated from the time informed consent is given until completion of the study and captured at each visit. Events occurring between signing of the informed consent form and dosing with study drug will be recorded on the medical history page of the eCRF. Events occurring from the time study drug is administered through EOS will be recorded on the AE page of the eCRF.									

STUDY PERIOD	Optional Prescreen	SCREENING	BASELINE & DOSING			FOLLOW-UP						
Visit	Prescreen	Screening ^a	Baseline	Randomiz Dosing S	ay 1 ation (3A) & ession (3B)	Day 2	Week 1	Week 2	Week 4	Week 8	Week 12 (or Early WD)/EOS	
Visit Number	N/A	1	2	3A	3B	4	5	6	7	8	9	
Timing or Permitted Window	none	Up to 30 days prior to Baseline	1-5 days prior to Day 1 ^{b, c}	Pre- dose	Dosing & post- dose	1 day after dosing	Day 8 ± 1 day	Day 15 ± 3 days	Day 29 ± 3 days	Day 57 ± 5 days	Day 85 ± 5 days	
Laboratory Procedures/Asse	ssment											

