## 5.7 Prior and Concomitant Medications, Psychiatric Medications and Non-drug Treatments

Prior and concomitant medications and psychiatric medications taken for GAD will be coded using World Health Organization (WHO) drug classifications, version March 2022 B3. Non-drug treatments will be coded using the Medical Dictionary for Regulatory Activities (MedDRA).

Prior medications are defined as medications that ended prior to the date of first dose of study drug administration (Day 1). Concomitant medications are defined as medications that started at any time but ended on or after the date of first dose (Day 1), including those that are ongoing at study completion. In the case of a missing or partial end date, in order to determine whether a medication is prior or concomitant, the following conservative imputation rule will be used: the unknown

portions of a medication end date will be imputed to the latest possible day or month. The imputed medication date will then be compared with the date of first dose to determine if the medication is prior or concomitant.

The number and percent of subjects using prior medications and concomitant medications will be tabulated by Anatomical, Therapeutic, and Chemical (ATC) Level 2 and by preferred name. Prior medications will be summarized separately from concomitant medications and will be reported by treatment group and overall, for the FAS and PPS populations. A subject listing of all prior and concomitant medications will be provided.

Psychiatric medications taken for GAD will be summarized by ATC Level 2 and preferred name and presented by treatment group and overall. Prior psychiatric medications will be summarized separately from concomitant psychiatric medications for the FAS and PPS populations. A subject listing of all psychiatric medications taken for GAD will be provided.

Non-drug treatments will be summarized by system organ class (SOC) and preferred term (PT) by treatment group and overall. Prior non-drug treatments will be summarized separately from concomitant non-drug treatments. A subject listing of all non-drug treatments will be provided.

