## 6.1.1 Handling of Missing Data and Potentially Biased Values

Missing data for the primary endpoint will be imputed using a multiple imputation approach assuming that the missingness mechanism can be retrieved from observed data. The imputation model will include the treatment group and the longitudinal sequence of HAM-A Total Score. Imputations will be performed 20 times using SAS PROC MI with the fully conditional specification (FCS) method.

For intercurrent events (IEs) the following methods will be used:

- The data recorded after the IE will be set to missing and imputed under a Missing Not at Random (MNAR) assumption by borrowing information from the placebo arm subjects (reference-based imputation) for the following:
  - Concomitant/prohibited medications that meet the threshold for impact = "Yes" during the impact assessment will be considered as the IE. Any observations after such an IE will be set to missing and will be imputed using the MNAR assumption.
- Available data will be used; missing data will be imputed under a Missing at Random (MAR) assumption, borrowing information from subjects in the same treatment arm for the following:
  - For IEs leading to study discontinuation due to other reasons
  - IEs related to the COVID-19 pandemic.

For missing data not due to IEs the imputation will be performed based on MAR assumption.

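### SAP 5.7 can tabulate a drug recorded as stopped before Baseline as concomitant when its stop date is partial, because the imputed date is checked only against Day 1

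*Protocol*

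**What the plan says.** Protocol 8.1.7 assigns each medication to an eCRF page by timing. Drugs taken at Baseline (Visit 2) or later "will be recorded in the concomitant medication eCRF". For the rest: "Medications stopped prior to Baseline (Visit 2) are recorded in the medication history eCRF". The Schedule of Activities (Table 2) repeats this: "Medications/therapies stopped prior to Baseline [Visit 2] are recorded in medication history". Table 2 places Baseline 1-5 days before Day 1.

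SAP 5.7 defines a prior medication as one that ended before the first-dose date and a concomitant one as one that ended on that date or later. For a missing or partial end date, the unknown "portions of a medication end date will be imputed to the latest possible day or month". Then: "The imputed medication date will then be compared with the date of first dose to determine if the medication is prior or concomitant". No condition on the eCRF page and no cap at Baseline is stated.

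The result feeds the prior and concomitant medication tables and the table of psychiatric medications taken for GAD: "Prior psychiatric medications will be summarized separately from concomitant psychiatric medications", in the FAS and PPS. The SAP addendum (section 1) says that it leaves the pre-planned analyses unchanged.

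**The concern.** Baseline precedes Day 1, so a history-page record marked as stopped before Baseline already shows that the drug ended before dosing. SAP 5.7 sets that information aside and can assign an end date that contradicts it.

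This trial is exposed because protocol 8.1.6 has subjects taper prohibited anxiolytics and antidepressants between Screening and Baseline. Their stop dates therefore fall close to Day 1, which is where filling to the end of the month goes wrong most often.

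At stake is the accuracy of the prior/concomitant split, above all for GAD psychiatric drugs. Protocol 8.1.6 gives removal of confounding of efficacy as one reason for the taper, and readers will use this table to judge whether that worked. With about 36 subjects per arm, one false entry moves an arm's percentage by 1/36 = 2.8 points.

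**Working it through.** The documents give no figure on this point. The check applies the SAP 5.7 rule to the calendar.

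**Inputs**
- Baseline is 1-5 days before Day 1, and Screening is up to 30 days before Baseline (Table 2).
- A drug still taken at Screening and stopped before Baseline therefore ended between 2 days (stopped the day before a Baseline held 1 day before Day 1) and 30 + 5 = 35 days before Day 1. Call this gap *g*.
- Rule: fill to month end if the day is unknown, or to 31 December if day and month are unknown. The drug is concomitant if the filled date is on or after Day 1.
- Assumption (not in the documents): Day 1 is spread evenly over a 365-day year.

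**Example.** The true stop is 6 March, recorded only as March, and Day 1 is 24 March. The filled date is 31 March, so the drug is classed as concomitant although it ended 18 days before dosing.

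**Day missing.** The error occurs when the stop and Day 1 share a calendar month. In a month of *L* days there are max(*L* - *g*, 0) such Day 1 dates. The share is the sum over the 12 months divided by 365, which for *g* up to 28 is (365 - 12*g*)/365.

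**Day and month missing.** The error occurs when the stop and Day 1 share a calendar year. The share is (365 - *g*)/365.

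| Gap (days) | Day missing | Only year known |
|---|---|---|
| 2 | 341/365 = 93.4% | 363/365 = 99.5% |
| 7 | 281/365 = 77.0% | 358/365 = 98.1% |
| 14 | 197/365 = 54.0% | 351/365 = 96.2% |
| 21 | 113/365 = 31.0% | 344/365 = 94.2% |
| 28 | 29/365 = 7.9% | 337/365 = 92.3% |
| 30 | 7/365 = 1.9% | 335/365 = 91.8% |
| 31 | 0% | 334/365 = 91.5% |
| 35 | 0% | 330/365 = 90.4% |

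**Average over gaps 2-35, weighted equally.** With the day missing, gaps 2-28 give 27 × 365 - 12 × 405 = 4,995 erroneous dates. Gap 29 gives 4 × 1 + 7 × 2 = 18 and gap 30 gives 7, for a total of 5,020. Divided by 34 × 365 = 12,410, this is 40.5%. With only the year known, the mean gap is 18.5 days and the average is 1 - 18.5/365 = 94.9%.

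**After the fix.** The cap is the day before Baseline, and Baseline is at least 1 day before Day 1. The capped date is therefore at least 2 days before Day 1, and the share is 0% at every gap.

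**The case against.** **Few of these dates may be partial.** Tapers are overseen by a site physician (protocol 8.1.6). Last doses must be checked against washouts set in days or half-lives (Table 5), and sites are asked to seek pharmacy records (8.1.5). A site can hardly confirm a washout of a few days from the month alone, still less from the year alone. Partial dates are likelier for older drugs, where the day-missing error is zero from 31 days on. This stands, and it makes the number affected unknown and probably small. It is not a guarantee: 8.1.5 lists duration of use among the medication-history items but names no stop date, whereas 11.10.6 requires start and end dates for concomitant medication.

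**The history page may not hold only stopped drugs.** Under 8.1.5 all therapies are assessed as part of the medication history. Treating every history-page record as prior would hide a drug that was never stopped. This stands and narrows the fix. The eCRF itself is not in the documents, and GAD psychiatric drugs may have a page of their own.

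**The rule is deliberately conservative.** Over-reporting concomitant use is the safer error when judging confounding, and a by-subject listing is planned. That justifies the rule where nothing else is known, but not where the record says that the drug had stopped. The rule could be read as bounded by the page, but the SAP does not say so, and literal programming would misclassify.

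**A stronger inference is tempting.** SAP 6.1.1 treats "Concomitant/prohibited medications that meet the threshold for impact" as the intercurrent event and sets later HAM-A scores to missing. A reader might infer that a false concomitant label could remove real scores from the primary analysis. The documents do not support this. The event depends on a separate impact assessment, and nothing says that it uses the end dates imputed under 5.7.

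**Conclusion.** The point holds as a defect in a stated rule for descriptive outputs. As written, SAP 5.7 can label as concomitant a drug that the eCRF records as stopped before Baseline.

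The shares in the table are conditional on the date being partial and on Day 1 being evenly spread over the calendar. They are not the share of all records affected, which cannot be derived from the documents. The rule also gives no value when the year is unknown, so that case is not covered here.

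The shown effect is confined to the prior and concomitant medication tables, including the GAD psychiatric one. No hypothesis test, estimand or safety analysis is shown to depend on it. It is a small, specific correction.

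**What to change.** In SAP 5.7, add a condition to the end-date imputation:
- For records on the medication history eCRF that are marked as stopped before Baseline, cap the imputed end date at the day before Baseline (Visit 2) and classify them as prior.
- Keep the existing latest-date rule for all other records, including history-page records not marked as stopped.
- Query any record whose known date parts conflict with the page on which it was entered.

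If GAD psychiatric medications are collected on a separate page, apply the same condition to records marked there as stopped before Baseline. This point calls for no change to SAP 6.1.1.

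The cost is a sentence or two and one programming condition. There is a small downside: a stopped-drug record entered on the wrong page would be accepted as prior unless the query catches it.
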